### 3.4 STUDY CALENDAR

Please refer to [Appendix A: Study Calendar](#).

### 3.5 COST AND COMPENSATION

#### 3.5.1 Costs

NIH does not bill health insurance companies or participants for any research or related clinical care that participants receive at the NIH Clinical Center. If some tests and procedures performed outside the NIH Clinical Center, participants may have to pay for these costs if they are not covered by insurance company. Medicines that are not part of the study treatment will not be provided or paid for by the NIH Clinical Center.

### 3.5.2 Compensation

No compensation will be provided for study participation.

### 3.5.3 Reimbursement

The NCI will cover the costs of some expenses associated with protocol participation. Some of these costs may be paid directly by the NIH and some may be reimbursed to the participant/guardian as appropriate. The amount and form of these payments are determined by the NCI Travel and Lodging Reimbursement Policy..

## **3.6 CRITERIA FOR REMOVAL FROM PROTOCOL THERAPY AND OFF STUDY CRITERIA**

Prior to removal from study, effort must be made to have all subjects complete a safety visit approximately 28-30 days after the last dose of study therapy.

### 3.6.1 Criteria for removal from protocol therapy

- Completion of study therapy
- Progressive disease
- DLT if clinically indicated.
- Intercurrent illness or medical circumstances.
- Voluntary withdrawal from the treatment regimen
- PI determines further treatment on this study is not in patient's best interest
- Patients who are off-treatment but still on-study will be followed as per the schedule in [Appendix A: Study Calendar](#), until they begin alternative therapy or voluntarily withdrawal from follow-up testing. Thereafter, they may be followed on-study for survival and other secondary endpoints.
- Positive pregnancy test

### 3.6.2 Off-Study Criteria

- Death
- Patient request to be withdrawn from study
- Non-compliance with study treatment and/or testing, or lost to follow-up, at discretion of PI

### 3.6.3 Lost to Follow-up

A participant will be considered lost to follow-up if he or she fails to return for 6 scheduled visits and is unable to be contacted by the study site staff.

The following actions must be taken if a participant fails to return to the clinic for a required study visit:

- The site will attempt to contact the participant and reschedule the missed visit for 3 months and counsel the participant on the importance of maintaining the assigned visit schedule and ascertain if the participant wishes to and/or should continue in the study.

- Before a participant is deemed lost to follow-up, the investigator or designee will make every effort to regain contact with the participant (where possible, 3 telephone calls and, if necessary, a certified letter to the participant's last known mailing address or local equivalent methods). These contact attempts should be documented in the participant's medical record or study file.
- Should the participant continue to be unreachable, he or she will be considered to have withdrawn from the study with a primary reason of lost to follow-up.

## **4 CONCOMITANT MEDICATIONS/MEASURES**

### **4.1 PERMITTED MEDICINES**

Any medications (other than those excluded by the clinical trial protocol) that are considered necessary to protect subject welfare and will not interfere with the trial medication may be given at the Investigator's discretion.

### **4.2 PROHIBITED MEDICINES**

**The following treatments must not be administered during the trial:**

- Immunotherapy including interferon, immunosuppressive drugs (for example, systemic corticosteroids except for short term treatment of allergic reactions, endocrine replacement therapy at low dose prednisone [ $>10$  mg daily] or equivalent, or for the treatment of irAEs or other appropriate short-term steroid use), or other experimental pharmaceutical products. Short term administration of systemic steroid or other immunosuppressant such as infliximab or mycophenolate (that is, for allergic reactions or the management of irAEs) is allowed. Steroids with no or minimal systemic effect (topical, inhalation) are allowed.
- Prophylactic use of corticosteroids for infusion related reactions is prohibited.
- Herbal remedies with immunostimulating properties (for example, mistletoe extract) or known to potentially interfere with major organ function (for example, hypericin).
- Any live vaccine therapies for the prevention of infectious disease. Administration of inactivated vaccines is allowed (for example, inactivated influenza or SARS-CoV-2 vaccines, and locally approved COVID vaccines).

If the administration of a non-permitted concomitant drug becomes necessary during the trial, the subject will be withdrawn from trial treatment.

## **5 CORRELATIVE STUDIES FOR RESEARCH**

### **5.1 BIOSPECIMEN COLLECTION**

Please refer to Section [5.2](#) for sample collection and timepoints.

#### **5.1.1 Immune Monitoring and Peripheral Immune Subset Analysis**

Peripheral Blood Mononuclear Cells (PBMCs) will be analyzed for changes in standard immune cell types (T-cell receptor clonality, CD4 and CD8 T cells, natural killer [NK] cells, regulatory T

*Abbreviated Title: Phase II M7824 in UC*

*Version Date: 06/23/2021*

cells [Tregs], myeloid-derived suppressor cells [MDSCs], and dendritic cells) as well as 123 immune cell subsets, as described elsewhere [39, 40].

PBMC analysis may include phenotypic and functional analysis of immune-cell subsets (such as CD4 and CD8 T cells, NK cells, Tregs, and MDSCs) including proliferation, cytokine production, lysis, and suppression using multicolor flow cytometry based assays.

#### **Collection and handling:**

For PBMCs collection, six 10mL sodium heparin (green top) tubes will be used.

#### 5.1.2 Comprehensive Cytokine/Chemokine analysis

To evaluate for circulating systemic levels of cytokines, chemokines of patients on treatment and correlate levels and changes with clinical activity of the study drug, plasma will be collected per PI discretion:

1. Plasma may be analyzed pre- and post-therapy for the following soluble factors: sCD27, sCD40 ligand using assays adapted to ECL platform.
2. Plasma may be analyzed for changes in cytokines (IFN- $\gamma$ , IL-6, IL-8, TNF- $\alpha$ , etc.), chemokines, antibodies, tumor-associated antigens, and/or other markers using ELISA or multiplexed assays (e.g. Mesoscale, Luminex, cytokine bead array).

#### **Collection and handling:**

For plasma collection, one 4 ml lavender top EDTA tube will be used..

### 5.1.3 Circulating cell-free DNA (cfDNA) isolation

The primary purpose of these studies is to evaluate for circulating cell-free DNA (cfDNA) of patients on treatment and correlate levels and changes with clinical activity of the study drug combination.

- Blood draw and storage
  - Draw 2 X 10 mL blood samples to EDTA tubes (lavender tops) follow the manufacture's instruction.
  - Remove tube from adaptor and immediately mix by gentle inversion 8 to 10 times. **CRITICAL STEP:** Do not shake or vortex tubes as cellular lysis could occur.
  - Tubes should be stored and transport at room temperature for up to four (4) hrs. Do not freeze.

### 5.1.4 HGF and Met

Plasma will be collected to determine whether plasma HGF and Met levels are biomarkers for metastatic non-prostate genitourinary tumors and/or response to treatment.

#### **Collection and handling**

10mL of whole blood collected in one 10mL EDTA tube at room temperature will be collected at each time point. Plasma samples will be stored by [name] laboratory and processed and analyzed by [name] laboratory.

### 5.1.5 Circulating Tumor Cells (CTCs)

To evaluate and characterize changes in expression of immune-related markers on CTCs. All patients enrolled on study will have CTC's measured using Epic Science's "no cell left behind" platform [41].

#### **Collection and handling**

CTC Samples should be collected in the 10 mL Streck Cell-Free DNA BCT. These tubes are commercially available through Streck (Omaha, NE).

*Abbreviated Title: Phase II M7824 in UC*

*Version Date: 06/23/2021*

**IMPORTANT:** The first 5 mL of blood collected from the fresh venipuncture cannot be used for the collection into the Streck tubes due to possibility of contaminating epithelial cells during venipuncture. Please ensure that at least one blood tube of 5 mL or more is collected prior to collection of the CTC sample to avoid adversely affecting the test results.

#### Prevention of Backflow:

Since Streck Cell-Free DNA BCT tubes contain chemical additives, it is important to avoid possible backflow from the tube. To guard against backflow, observe the following precautions:

- Keep patient's arm in the downward position during the collection procedure.
- Hold the tube with the stopper uppermost.
- Release tourniquet once the blood starts to flow into the tube, or within 2 minutes of application.
- Tube contents should not touch stopper or the end of the needle during the collection procedure.

#### **Blood Collection Instructions:**

**\*\*Arrange for the same day shipment!**

- Confirm blood tube is not expired. Expired tubes should not be used for blood collection.
- Draw whole blood sample into 10 mL Streck Cell-Free DNA BCT tube (\*see note regarding prevention of backflow). Fill tube until blood flow stops. NOTE: Epic requires a minimum of 4 mL blood per sample, but a full 10 mL tube of blood should be provided when possible.
- Remove tube from adapter and immediately mix by gentle inversion 8 to 10 times. Tube inversion prevents clotting. Inadequate or delayed mixing may result in inaccurate test results.
- Label the tube with subject's identification and date and time of blood draw. Unlabeled blood tubes may not be processed.
- Keep sample at room temperature and ship on day of collection in shipper with ambient gel packs.

#### 5.1.6 c-Met analysis by RT-PCR

Peripheral blood for analysis of c-Met mRNA will be collected in a PAXgene tube (PreAnalytix; 2.5 cc peripheral blood per tube) per the manufacturer's instructions. After the blood is drawn, the tube should be inverted several times, placed at 4°C. RNA will be isolated using the PAXgene Blood RNA Kit according to the manufacturer's instructions. The first strand cDNA will be synthesized from total RNA by using a HC reverse transcription kit (Applied Biosystems). The reaction mixture is diluted to 100 µL with TE. PCR will be performed using the c-met primers).

#### 5.1.7 Tumor Studies

##### 5.1.7.1 RNA-Seq, TCR sequencing, and MET Protein

- **Single Cell RNA-Seq:** from RNA extracted from fresh frozen tumor tissue for transcriptome sequencing (RNA-Seq) to evaluate if RNA gene expression profiling that measure responsive genes relative to antigen presentation, chemokine expression, cytotoxic activity and adaptive immune resistance are correlated with clinical response.
- **TCR Sequencing:** from RNA extracted from fresh frozen tumor tissue: To evaluate and characterize the clonality of the T-cell population as a way to infer the peripheral expansion of tumor-reactive T-cell clones in response to study drug combination.

*Abbreviated Title: Phase II M7824 in UC*

*Version Date: 06/23/2021*

- **MET protein:** MET protein evaluated from tumor biopsies will be correlated with clinical responses

Tumor tissue will be prioritized (highest to lowest):

1) Formalin fixed for diagnostic and DNA/RNA extraction from FFPE (20 slides total)

- 10 unstained FFPE slides (room temperature) will be sent to Laboratory of Pathology. Please contact [name] ([[contact]](mailto:[contact])), prior to transport. [contact].
- 10 unstained FFPE slides (room temperature) will be stored in the Laboratory of Pathology for additional tumor testing

2) Three cores will be collected when possible and flash frozen for RNA extraction

- For frozen tumor, place 1 core in 1.5mL Eppendorf or 15mL conical tube or 1-2 blocks on dry ice. DNA and RNA extracted by Laboratory of Pathology and sent to Oncogenomics Section for exome sequencing, and TCR sequencing (contact [name], [[contact]](mailto:[contact])). Single Cell RNA Seq will be performed in the Single Cell Analysis Facility (SCAF) (contact [name], [[contact]](mailto:[contact]) / [contact]).
- 1-2 frozen cores will be stored by [name] lab for additional testing. Please contact [name] ([[contact]](mailto:[contact]) / [contact]) to arrange for pick-up of sample)

#### **FFPE:**

In the case of existing (pre-treatment) FFPE slide/blocks already available for the consenting patients, the sample will be transferred to the Laboratory of Pathology (LP).

#### **Collection and handling**

For DNA and RNA to be extracted from FFPE tissues the Laboratory of Pathology in consultation with the surgical pathologist will evaluate specimen for adequacy and diagnosis. For the majority of cases the Laboratory of Pathology will perform both the extraction and quality control (QC) of nucleic acids. This will include DNA and RNA from tumor, and DNA from germline tissue (matched normal, blood, or other tissues). The DNA will be used for exome sequencing, and RNA sequencing will be performed in a research setting. Final approval to proceed to sequencing will be determined by passing all QCs according to the SOPs.

#### **Fresh/Frozen Tissue:**

If a pre-treatment biopsy is performed, the surgical sample will be obtained by the interventional radiology or surgical dissection/resection, and the sample collection will be processed as follows:

**Interventional Radiologist:** Recommend 19 gauge needle or larger in caliber after discussion and at the discretion of the intervention radiologist

Contact Research Nurse or [name] to be present at time of procedure.

*Abbreviated Title: Phase II M7824 in UC*

*Version Date: 06/23/2021*

1. 1-2 cores snap frozen sent to OncoGenomics (contact [name], [[contact]](mailto:[contact])). Transport to OncoGenomics in 4°C wet ice.
2. 1-2 cores in container cooled in dry ice for flash freezing. Transport to [name]'s lab in dry ice. (contact [name], [[contact]](mailto:[contact])).

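### Section 5.1.7.1 sends snap-frozen pre-treatment cores to OncoGenomics on 4°C wet ice, against its own dry-ice handling, and leaves open whether cores or extracts are shipped

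*Combined protocol and SAP*

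**What the plan says.** Section 5.1.7.1 describes frozen tumor tissue in two places.

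The general text on tissue priority says: "Three cores will be collected when possible and flash frozen for RNA extraction". It continues: "For frozen tumor, place 1 core in 1.5mL Eppendorf or 15mL conical tube or 1-2 blocks on dry ice". On routing it says: "DNA and RNA extracted by Laboratory of Pathology and sent to Oncogenomics Section for exome sequencing, and TCR sequencing". Single-cell RNA sequencing is assigned to a separate facility, and one or two further frozen cores are stored by another laboratory.

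The later Fresh/Frozen Tissue text opens by limiting itself to the case where a pre-treatment biopsy is done. Its item 1 reads "1-2 cores snap frozen sent to OncoGenomics", followed by "Transport to OncoGenomics in 4°C wet ice". Its item 2 reads "1-2 cores in container cooled in dry ice for flash freezing", and those cores then also travel in dry ice.

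The Sample Transport/Storage text that follows has the Laboratory of Pathology arrange transport of DNA and RNA, and names RNA from fresh frozen tumor as the input for TCR sequencing. In Section 5.2 the frozen core for TCR sequencing is listed against the Laboratory of Pathology, at baseline and again between cycles 2 and 4.

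**The concern.** Wet ice at 4°C is above freezing. A core that has been snap frozen and is then carried on wet ice will not arrive frozen, which defeats the purpose of freezing it. The stated purpose is RNA extraction, and thawing tissue with no stabiliser before extraction puts that RNA at risk. The protocol names no stabiliser, sets no transit limit and gives no reason for wet ice.

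What is at stake is tissue from an invasive procedure and the tumor TCR readout of exploratory objective 2, which is meant to describe T-cell clonality in response to the drug. Staff reading the section also cannot tell whether OncoGenomics should receive a frozen core or extracted nucleic acid. Someone who follows the wet-ice line may lose RNA quality, and someone who uses dry ice departs from the written procedure.

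**Working it through.** The protocol gives no figure to reproduce here, and no sample size, error rate or power depends on the point. The check compares the instructions and then counts the cores exposed.

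**Temperature**
- Fresh/Frozen Tissue, item 1: snap frozen, then 4°C wet ice.
- Fresh/Frozen Tissue, item 2: flash frozen in dry ice, then dry ice.
- General text of 5.1.7.1: frozen tumor on dry ice.

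Item 1 is the only one of the three that puts frozen tissue above 0°C, and it does so for tissue in the same stated condition.

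**What is shipped**
- Fresh/Frozen Tissue, item 1: cores go to OncoGenomics.
- General text of 5.1.7.1: the Laboratory of Pathology extracts, and nucleic acid goes to OncoGenomics for exome and TCR sequencing.
- Sample Transport/Storage: the Laboratory of Pathology arranges transport of DNA and RNA. The destination given is the Genetics Branch, whose relation to OncoGenomics is not stated.
- Section 5.2: the TCR core is listed against the Laboratory of Pathology.

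Item 1 again stands alone. On the other three, no frozen core needs to travel to OncoGenomics.

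**Which assay**
- OncoGenomics is given exome and TCR sequencing, and TCR sequencing uses RNA from fresh frozen tumor. The link to TCR is therefore direct.
- Single-cell RNA sequencing is done elsewhere. Sample Transport/Storage also plans RNA-Seq from frozen tumor but does not say that it uses the item 1 cores.

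**Which time point**
- Item 1 sits under a condition that restricts it to pre-treatment biopsies. Read literally, on-treatment cores fall under the general dry-ice text.

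**Number of cores**
- Evaluable patients if every cohort completes both stages (Section 10.2): 15 + 16 + 16 + 21 = 68.
- Cores per pre-treatment biopsy under item 1: 1 to 2.
- Upper bound: 68 × 1 = 68 to 68 × 2 = 136 cores.
- If every cohort stopped after stage 1: 9 + 8 + 12 + 12 = 41 patients, so 41 to 82 cores.
- Criterion 2.1.1.8 accepts archival tissue in place of a new biopsy, which lowers either count by an amount the documents do not give.

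**The case against.** The strongest reply is that most of the section already gives a workable route. If the Laboratory of Pathology extracts before anything goes to OncoGenomics, no frozen core travels on wet ice and nothing thaws. The 4°C line may also be a slip for unfrozen tissue, since the sub-heading covers fresh and frozen material together. There are partial back-ups: FFPE tissue has first priority for DNA and RNA extraction, ten further slides are stored, and one or two frozen cores are held elsewhere. The readouts are exploratory and analysed descriptively.

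All of this limits the consequence, but it does not remove the conflict. Under either explanation the words in item 1 are wrong: the temperature if the cores are frozen, or the description of the cores if they are not.

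The reply does defeat several stronger inferences that a reader might draw:
- *The RNA will be degraded.* The documents give no transit time, and on the general routing extraction comes first. Only a risk is supported.
- *The transcriptome readouts are lost too.* Single-cell work is done at another facility, and the other RNA-Seq is not tied to these cores.
- *On-treatment cores should be counted as well, doubling the total.* Item 1 is confined to pre-treatment biopsies, and on-treatment biopsy is waived where not feasible (Section 5.1.7.2; Appendix A, note 1).
- *Paired changes are biased.* Variation in transit unrelated to time point adds noise or sample loss. Bias needs a systematic difference between time points. The literal wording makes that possible but does not show that it would occur.

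**Conclusion.** The point stands as an instruction that is wrong as written, together with an unresolved conflict over what is shipped. Followed literally, item 1 lets snap-frozen pre-treatment cores thaw and puts RNA at risk, chiefly for TCR sequencing. The upper bound of 68 to 136 cores assumes that every evaluable patient has a new pre-treatment biopsy, that all four cohorts complete stage 2, and that item 1 governs over the general routing. A further possible consequence is that baseline and on-treatment cores follow different rules in a comparison meant to show change.

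The inference from thawing to RNA damage is general reasoning about unstabilised tissue and is not stated in the protocol; its extent cannot be sized from the documents. The effect is confined to exploratory tumor correlatives. Objective response, PFS, OS, safety and the two-stage rules do not depend on it.

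**What to change.** In the Fresh/Frozen Tissue list of Section 5.1.7.1, replace the wet-ice sentence with: 'Snap-frozen cores remain on dry ice from freezing to receipt.' If the 4°C line was intended for unfrozen tissue, name that tissue and delete the words describing it as snap frozen.

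State once whether OncoGenomics receives frozen cores or nucleic acid extracted by the Laboratory of Pathology, and bring the general text of 5.1.7.1, the Fresh/Frozen Tissue list, Sample Transport/Storage and the Section 5.2 table into line with that statement.

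Say that the same handling applies to baseline and on-treatment cores.

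The cost is a short text correction. Dry ice is already part of the procedure for the other frozen cores, and no endpoint, sample size or analysis changes.

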### **Sample Transport/Storage:**

Laboratory of Pathology (LP) will arrange transportation of the DNA (and RNA sample) to the Genetics Branch. [name]. Please contact [name] ([[contact]](mailto:[contact])), prior to transport. [contact]. [name] will ensure that the patient has been consented and that he has been emailed a copy of the consent form before the samples are processed for RNA sequencing

The primary purpose of the studies is to utilize Omics high throughput techniques to identify novel biomarkers and targets of response to this study drug.

- **Transcriptome sequencing (RNA-Seq)** from RNA extracted from blood and fresh frozen tumor tissue: To evaluate if RNA gene expression profiling that measure responsive genes relative to antigen presentation, chemokine expression, cytotoxic activity and adaptive immune resistance are correlated with clinical response.
- **T-cell receptor (TCR) sequencing** from RNA extracted from fresh frozen tumor tissue: To evaluate and characterize the clonality of the T-cell population as a way to infer the peripheral expansion of tumor-reactive T-cell clones in response to study drug.

#### 5.1.7.2 Genomics studies– TrueSight Oncology

Pre-treatment tissue biopsy and/or tissue availability is mandatory. On-treatment biopsy is required unless obtaining biopsy is not technically or clinically feasible. Post-treatment biopsy is optional.

- 10 unstained FFPE slides (room temperature) from in-house surgery and outside materials will be brought directly to General Surgical Pathology office - [name].

Paraffin-embedded tissue specimens from outside must be formalin fixed. They will be submitted either as a tissue block containing >20% tumor, or a minimum of 10 FFPE unstained slides for molecular pathology testing and surgical pathology review.

Alterations to the above requirements on sample submission will be at the discretion of the Laboratory of Pathology.

The TruSight Oncology 500 (TSO-500) is a next-generation sequencing (NGS) assay that analyzes cancer-relevant genes from both DNA and RNA in one integrated workflow. During library preparation, enrichment chemistry is optimized to capture nucleic acid targets from formalin-fixed, paraffin-embedded (FFPE) tissues. With simultaneous analysis of both DNA and RNA, various types of biomarkers relevant to a given tumor type (single nucleotide variants (SNVs), indels, fusions, splice variants, tumor mutation burden (TMB), and microsatellite instability (MSI)) can be assessed from the same sample in a single assay. The RNA panel uses a probe design that enables capture of both known fusions and novel fusion partners. The TSO500 panel includes 523 genes for DNA mutation detection and 55 genes for fusion and splice variant detection.

*Abbreviated Title: Phase II M7824 in UC*

*Version Date: 06/23/2021*

The new molecular pathology report is also incorporated with reporting software for clinical actionability as Tier levels of FDA-approved drug and clinical trials, and pathogenicity based on AMP/ASCO/CAP/ACMG guidelines.

NIH Clinical Record Interactive System (CRIS) orders will be placed to notify the laboratory of pathology.

